## 11. RECRUITMENT

This study involves randomization at the geographic cluster rather than individual level. While individual randomization is more powerful, cluster randomization allows us to reduce risk for contamination that may occur if both treatment conditions were offered in the same geographic area. Participating couples will be recruited from geographic clusters of approximately equal size mapped for randomization. Clusters are geographically distinct areas with administrative boundaries, natural borders and appropriate distance from other study clusters to reduce risk for contamination. Clusters will be created based on geographic boundaries, population density (approximately 5000 population per cluster), and proximity to ANMs and health providers. Clusters will be selected based on minimum number of eligible couples (at least 60 eligible couples); clusters will then subsequently be randomized to intervention or control conditions using computer-generated random numbers. Households within each cluster will be screened sequentially for eligibility. Research staff are not to be blinded to the treatment condition assignment to clusters. Recruitment of eligible households will be n = 60 per cluster. In a small cluster if the total number of eligible couples is equal to 60, all couples are approached for recruitment. In a larger cluster if the eligible couple number is more than 60, the required number of couples will be selected through systematic random sampling (selecting every nth participant).

Trained NIRRH survey research teams (1 male & 1 female) will approach selected households for screening and recruitment. Three attempts to reach the couple will be made for each selected household. If an eligible household has two or more couples meeting eligibility criteria, a Kish Grid will be used to determine the participants. Couples selected from eligible households will be asked to join the study and will be informed that the study focuses on FP. Data will be collected to assess participation rates and biases by

age, and contraceptive use. Recruitment/enrollment and intervention delivery will occur over 2.5 years on a rolling basis.

**PLEASE NOTE:** No identifiable information will be collected from those screened and found to be ineligible or unwilling to participate, across study phases.

## **12. INFORMED CONSENT**

Recruitment and written consent (hard copy) will be implemented by trained Masters-level research staff for all phases of study; research staff and participants will be gender-matched. For every source of primary data collection, written informed consent will be acquired prior to data collection. For RCT study participants, consent will be obtained prior to screening, survey, and, for women, urine pregnancy testing; consent will include follow-up data collection. For IDI participants, written informed consent will again be provided prior to interviews; all IDIs are 1-time events. Stakeholders providing IDI (Aim 3) will provide verbal informed consent prior to participation; verbal consent will be used to facilitate use of phone interviews since no personal questions will be included in these interviews.

It must be noted that issues of literacy are a major concern in rural India, particularly for women. [name] and other Co-Is on this study have years of experience obtaining written informed consent with both illiterate and literate men and women in rural India. In the case of illiterate men/women, the consent form will be read in the presence of a trusted literate adult (18 years or older) of the participant's choosing, and then the individual will be asked in the presence of that adult whether they are willing to participate. Research staff will provide explanations to all queries, and anything that cannot be answered in the field will be addressed via telephone contact with [name].

The consent forms and survey forms will be prepared in Marathi language. Written consent will be required, as our in-country research partner NIRRH prefers written informed consent, rather than verbal consent, in behavioral studies involving sensitive research questions, such as those used in the current study. Although females aged 18-21 years will likely be included in this study, parental consent for their participation will not be obtained, as all of these females will be wives and are thus recognized as adults capable of providing consent for themselves in the Indian context.

## **13. ALTERNATIVES TO STUDY PARTICIPATION**

There will be no required alternative treatments or procedures for study participants or those ineligible or declining participation. However, all husband and wife participants will be provided with information regarding local antenatal services and primary health center family planning services, available through the state public health system and National Rural Health Mission.

## **14. POTENTIAL RISKS**

Questions included in qualitative and quantitative assessments with men and women may be embarrassing or emotionally upsetting to participants as they assess sexual and contraceptive behaviors, and for women, physical and sexual violence from husbands. Embarrassment is reduced by the brevity of the research tools and the use of matched-gender and well-trained research interviewers. Also, assessments of abusive or controlling behavior from husbands are asked of wives confidentially, and not from husbands. Wives and husbands will be recruited from the same households, but in accordance with the World Health Organization's "Ethical and Safety Recommendations for Research on Domestic Violence Against Women", only wives will be assessed for domestic violence. These recommendations guide against asking husbands about perpetration or informing husbands of what wives are being asked, to reduce risk for violence. Husbands will be asked about their attitudes toward domestic violence, including marital sexual violence (MSV), a targeted outcome of the CHARM2 intervention. Wives will be asked about their marital sexual experiences including MSV as part of intervention sessions with ANMs or trained providers/counselors; again, this can create discomfort or potential vulnerability to violence if the husband learns of this disclosure. Wives will be discouraged from sharing both the nature of the questions and their responses in surveys and intervention sessions, with their husbands or others, and researchers will not share this information with husbands. To further protect wives, we will follow protocols used in our prior intervention studies on domestic and sexual violence to reduce risk for wives; these protocols are consistent with the World Health Organization's "Ethical and Safety Recommendations for Research on Domestic Violence Against Women."

It is possible that some participants may become anxious, depressed, or angry due to study or intervention content, and there is a small possibility this may result in their becoming a risk to themselves or someone else. Our previous work in rural and urban Maharashtra, inclusive of wives and husbands and assessing similar items and using a similar approach, elicited no such responses. However, to ensure the safety of our participants and staff, precautions will be taken to minimize participants' risk of emotional distress. Prior to assessment, participants will be reminded that they are free not to answer a question and may terminate their participation at any point. If indications of distress are observed in an individual, the participant will be privately debriefed and screened for emotional distress: "These questions (or discussions) can make some people feel sad, anxious, or angry. How are you feeling now?" If it is determined that the participant is in need of immediate assistance, the individual will be immediately escorted to a mental health provider at the closest available health center. In addition to this debriefing, all participants will be provided with referrals, in the form of a list of local programs for family planning and, for wives only, domestic violence.

**Loss of Confidentiality:** There is the potential that researchers may be required to breach participants' confidentiality if participants disclose any intentions to hurt themselves or others, report child or elder abuse, or report homicidal intention or perpetration. Our research instruments do not ask this information, so there should be minimal risk about eliciting such a response from the participant. However, it is possible that participants may disclose this information during an intervention session or following survey completion

and during our debriefing which involves screening for emotional distress. The consent form will clearly outline for each participant conditions under which such a breach of confidentiality may occur; and will be covered prior to any survey assessment or interview.

In addition to risks to wives, there are also risks to CHARM2 providers and stakeholders participating in this study, as any criticism they provide can make them vulnerable to the public health system in which they may work or intersect. We will work to compile questions that are more objective than opinion in nature, with regard to care provision, health care and government infrastructures, and CHARM2 implementation and supervision, to reduce this risk. We also will assure confidentiality to participants. For anyone who is no longer comfortable participating in the study, they may withdraw from participation without penalty. CHARM2 providers who withdraw from the study lose no financial support from this discontinuation, as financial support is not given to providers for their participation in CHARM2.

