
## **6. SPECIFIC AIMS**

1) To implement the CHARM 2 GE+FP intervention, comprised of CHARM sessions with men and parallel sessions with women, and inclusive of broader contraceptive options including LARC, as well as one combined couples session. Men's sessions will be delivered by male health providers; women's sessions will be delivered by public Auxiliary Nurse and Midwives (ANMs), or a trained provider/counselor. The couple's session will be delivered by an ANM, trained provider, or counselor.

2) To evaluate the impact of CHARM2 on spacing contraceptive use (including LARC), unintended pregnancy, and MSV via a two armed cluster RCT with N=1200 married couples from 20 geographic clusters (n=60 couples per cluster) in rural India. The control arm will receive SOC in the form of community health workers offering pills/condoms and linking women to public health clinics. Outcomes will be assessed via pregnancy testing and surveys at baseline, 9 and 18-month follow-ups.

**Hypotheses:** We hypothesize that CHARM2 participants will be more likely than SOC participants to:

- a) Use contraception (including LARC) at 9 & 18-month follow-ups; effects on LARC will be explored
- b) Be less likely to report marital sexual violence (MSV) at 9 & 18-month follow-ups
- c) Not have an unintended pregnancy over the 18-month follow-up period.

3) To assess the quality, scalability, and replicability of CHARM2 for uptake by rural health systems (i.e., sustainability), using implementation science methods including IDI with CHARM2 couples (n=50) and providers (n=20), 5-7 focus groups with MILs of couples that participate in IDIs, control condition couples (n=20), and key stakeholders from the FP and rural health infrastructures at state, national and international levels (n=50), survey of healthcare facilities in the study area (n approximately=250), and a cost-effectiveness analysis.

Should CHARM2 prove effective and sustainable, study findings will have broad implications for FP interventions for low resource settings in India and elsewhere.

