## 9. RESEARCH DESIGN AND METHODS

**Overview:** This study will involve 3 phases: Phase 1- the Preparatory Phase to map the project area and prepare communities for the planned research. Phase 2- Implementation and Evaluation of CHARM 2 (Aims 1&2), using a two-armed cluster randomized controlled trial (RCT) in 20 geographic clusters mapped in Phase 1. To assess treatment impact on contraceptive use, MSV and unintended pregnancy, clusters will be randomized to receive CHARM2 or the control program, which includes SOC public health FP services. Intervention effects will be assessed via surveys and pregnancy testing at baseline and 9 &18-month follow-up with n=1200 couples (wife 18-29 years). Phase 3- Implementation Science Assessments will include IDI with CHARM2 providers (n=20), select CHARM2 couples (n=50), MILs for those IDI couple participants that are comfortable with MIL participation, control condition couples (n=20), and key Indian stakeholders in FP & public health (n=50). Interviews with providers and couples will explore intervention delivery and perceived impact. Interviews with FP & public health stakeholders will obtain feedback on perceived feasibility to sustain and scale up CHARM2. A survey of all healthcare facilities in the study area (n approximately=250) will support understanding of the local healthcare context as well as access to and availability of family planning in the study communities. A cost-effectiveness analysis will also be done to support considerations of sustainability.

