**The CHARM2 Intervention:** CHARM2 intervention will involve gender, culture and contextually-tailored FP+GE counseling sessions delivered individually to husbands by a trained male health provider (2 sessions), and, in parallel, delivered individually to wives by a trained female ANM or trained provider/counselor (2 sessions), as well as a combined couples session. CHARM2 differs from the original CHARM intervention by adding parallel sessions for wives, delivered by the ANM, and including LARC counseling for husbands and wives and opportunity for LARC provision in the sessions with women. The ANM or trained provider/counselor session will use GE counseling from the CHARM couple session with public health FP and LARC counseling. Sessions will be provided at the participants' home or within the clinical setting, as the husband and wife prefer. The 5 sessions will be delivered across 3 months with a minimum of 1 week between the men's sessions; the men's Session 1 must be delivered before the female session.

**SOC Control Condition:** Under India's public health system, ASHAs and ANMs provide household visits to women to increase awareness and use of FP services, with ASHAs incentivized to bring women to PHCs for FP services and ANMs rarely providing contraceptives. For those women or couples that reach the PHC, SOC FP counseling and services are delivered by a physician; free contraceptives are then offered, most often female sterilization and rarely LARC. Control group female participants will be linked with ASHAs to support access to PHC FP services. ANMs will not provide LARC or GE counseling for control condition women. Men will receive no FP counseling.

**Timeline:** Phase 1 of the study preparation will take approximately 3 months. Phase 2 will be in month 4 to month 60, including enrollment and intervention start at month 4, 9 month follow up at month 13, and 18 month follow up at month 22. The outcome analysis will also be carried out in this phase at month 40. Phase 3, on sustaining the intervention, will overlap from month 7 to month 60.

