## **Quantitative Data Collection:**

Survey and urine pregnancy test data (from wives) will be collected from all enrolled couples in the CHARM2 RCT evaluation study. Both intervention and SOC arm participants will provide survey data at baseline and 9 & 18 month follow-ups. Survey data will be collected electronically on tablets using a unique identifier to link data between couples and across time. Wives in both the intervention and the SOC arms will be tested for pregnancy using a urine specimen at baseline and at both post-test timepoints; these data will directly be entered into the password protected electronic survey system at the time of survey data collection. Urine samples for pregnancy testing will not be retained for the study, but will be disposed of in disposal facilities upon completion of the test. Survey and pregnancy test results data will be stored locally on the tablet and, when internet is available, uploaded to the password-protected server. Separately, a list of contact names with unique identifiers will be maintained for tracking purposes; a hard copy form of this list will be kept in a locked file in [name] locked office at NIRRH. Baseline and follow-up surveys will be collected from couples using measures from the original CHARM study, which was based on India's Demographic and Health Survey (DHS/India's NFHS-3) and other validated measures. Couples must meet the eligibility criteria outlined below.

Eligible couples will be:

- Young wives (aged 18-29 years) and their husbands
- couples fluent in Marathi and both willing to participate
- no sterilization or infertility indicated (infertility is defined as having no pregnancy for 1+ years despite non-use of traditional or modern contraception)
- no pregnancy or female/male surgical sterilization planned for the next 18 months, and no reported use of consistent use of modern contraceptives in the past three months, and
- residing in the village for at least 2 years and residing together for at least 3 months, to facilitate follow-up tracking

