The primary analyses will use an intent-to-treat approach and analyze all subjects according to randomized group. For subjects missing month 9 or 18 endpoints, these will be multiply imputed from the lower (worse) half of the distribution from their arm (conservative approach). Additional analyses will be conducted using a per protocol approach that includes only those subjects who complete the full intervention. Analyses will use women's data only; however, men's data will be used to validate outcomes a) increased contraceptive use, and b) reduced unintended pregnancy. Exploratory analyses using outcomes of contraception by type (e.g., LARC) may be conducted if numbers are sufficient across time-points.

At 18 month follow-up, healthcare facilities in the study area will be surveyed to assess provision of FP counseling and methods, availability of FP methods, approximate FP method client volume, provider type/qualifications, and participation in the CHARM2 intervention. Healthcare facility location GPS will be collected for mapping of healthcare services in the study area; no personally identifying information regarding the providers will be collected.

At 18 month follow-up, participants' location data will be re-collected in the form of GPS coordinates; this data will be used to examine distances to healthcare facilities in the study area. GPS data will be collected in a separate survey form to be accessed only by NIRRH in-country study staff. In-country study staff may use this location data, in conjunction with healthcare facility location data, to calculate participant-level distance to healthcare providers. Geolocation data will **not** be shared with UCSD or any other external sources; any maps produced which visualize healthcare facility location and access will **not** include participant locations. Calculated distances **only** may be shared with UCSD analysts, to be summarized and utilized in adjusted regression models to better understand drivers of and barriers to health care services generally, and family planning services specifically, in the study area.

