Participation in this study and programs is completely voluntary. If the participant feels uncomfortable or is upset by the interviews or surveys or intervention sessions, she/he may withdraw from the study as outlined by the consent form.

Only wives will be assessed for marital violence in the surveys and intervention sessions; they will be asked not to disclose participation in these items as it may put themselves or others at risk for violence as a consequence of study participation. Utmost confidentiality will be maintained by all research staff. Please see section below on "Protection from Loss of Confidentiality" for details. These protocols to protect women's confidentiality are in line with WHO guidelines on domestic violence research.

It must be noted that there is no law against marital sexual violence/rape in India at this time. [name] works closely with many groups in India that work on issues of domestic and sexual violence, including Amnesty International India and CEHAT, allowing this team to be abreast of the most up to date laws and services to support victims who are identified and wish to seek services. Our experience from the original CHARM study as well as other studies is that women rarely wish to obtain formal support against domestic violence.

**Protection from Loss of Confidentiality:** As noted in the section on Potential Risks, security of confidentiality is a primary means of reducing risks for our research participants. Hence, every effort will be made to minimize participants' risk of a loss of confidentiality during this study. Participants will not have family members or others informed of their participation in the study unless they choose to tell them. Participants from the same household or institution will not be informed of the survey questions or responses for other members of their household or institution, or the nature of the interventions offered. Only unique identifiers will be used to label data collected in this study; only NIRRH staff and Co-Is will have access to the identifiable information linked with the unique identifiers. These research staff will be required to maintain the confidentiality of all research participants, and will have signed a pledge to do so upon joining the research team.

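### Physical violence by husbands is a plausible harm of CHARM2, but only marital sexual violence is compared between arms, so no randomised estimate of physical violence is planned

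*Combined protocol and SAP*

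**What the plan says.** **Risk.** Section 14 describes wives being asked about MSV in sessions with the nurse-midwife or counsellor and warns that "this can create discomfort or potential vulnerability to violence if the husband learns of this disclosure". Section 18 also treats violence provoked by study involvement as something to prevent. In section 9, under the SOC control condition, "ANMs will not provide LARC or GE counseling for control condition women", so the session route exists in one arm only.

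**Measurement.** Section 14 says of the qualitative and quantitative assessments together that "they assess sexual and contraceptive behaviors, and for women, physical and sexual violence from husbands". Section 15 states: "Only wives will be assessed for marital violence in the surveys and intervention sessions". Section 9, Quantitative Data Collection, adds: "Both intervention and SOC arm participants will provide survey data at baseline and 9 & 18 month follow-ups".

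**Comparison.** The only violence hypothesis in section 6 is that CHARM2 participants will "Be less likely to report marital sexual violence (MSV) at 9 & 18-month follow-ups". The section 9 overview gives the purpose of randomisation as "To assess treatment impact on contraceptive use, MSV and unintended pregnancy". The power section covers the same three outcomes, and Data Analysis adds no other.

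**Other handling of violence.**
- Section 15 provides safety planning, supported referral and debriefing for women who report spousal violence, and withdrawal from the study when the violence is life-threatening.
- Section 15 also sets up a yearly DSMB safety review, with no violence measure named.
- Section 18 treats violence found to result from participation as an adverse event, with study termination as the last resort.
- Section 9 plans interviews with 50 CHARM2 couples and 20 control couples that touch on violence.

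**The concern.** Physical violence by husbands also occurs without the study. The stated trigger in section 18 depends on judging that violence resulted from participation. For a harm with a background rate, such a judgement cannot show an excess; only a comparison with the randomised control arm can.

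The stake is the safety evidence beside the efficacy results. The trial could report less MSV and support scale-up with no planned estimate of what happened to physical violence. An intervention that challenges household decision-making could move the two in different directions.

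Withdrawal for life-threatening violence adds to the problem. The most severely affected women may be missing from the 9- and 18-month surveys, and an excess of such withdrawals under CHARM2 would make the remaining data understate harm.

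**Working it through.** **Inputs from the documents.** 20 clusters, hence 10 per arm; 48 observed couples per cluster, so 960 in total and 480 per arm. MSV-free 89.2% vs 95.2% with kappa 0.036; contraception 40% vs 52% with kappa 0.10; no unintended pregnancy 90% vs 95.5% with kappa 0. Kappa is split equally between village and cluster.

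**Assumptions.** Control rate of physical violence 10% to 30%; 12 couples per village; kappa between 0 and 0.10, borrowed from the other outcomes; two-sided 5%. The documents give none of these for physical violence.

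**Formulas.** With kappa (k) read as a logit-scale variance, each level has rho = (k/2) × p × (1 − p) at the control rate p. Design effect D = 1 + 11·rho + 47·rho. SE = sqrt(D × [p1(1 − p1) + p2(1 − p2)] / 480). Normal-approximation power = Φ(difference/SE − 1.96).

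**1. The plan's own power.**
- MSV: rho = 0.018 × 0.108 × 0.892 = 0.00173; D = 1 + 58 × 0.00173 = 1.10; SE = 0.0180; 0.06/0.0180 = 3.32; power 91.4% (stated 91.5%).
- Contraception: rho = 0.05 × 0.24 = 0.012; D = 1.70; SE = 0.0416; power 82.3% (stated 83.3%).
- Unintended pregnancy: D = 1; power 91.1% (stated 89.5%).

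This does not settle what kappa means. Read as a between-cluster coefficient of variation, with 9 in place of 10 clusters per arm as a small-sample correction, it gives 91.0%, 84.8% and 88.0%, which is about as close. Read as a direct intra-cluster correlation (D = 1 + 47k) it gives 57% for MSV and 35% for contraception, so that reading is set aside.

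**2. Precision for physical violence.** The half-width is the critical value × SE with both arms at the control rate. In each pair the first figure uses the normal value 1.96; the second uses t on 18 degrees of freedom (2.101; power by noncentral t), because there are only 20 clusters.

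| Control rate, kappa | D | 95% CI half-width (points) | Power, +5 points | Power, +10 points |
|---|---|---|---|---|
| 10%, 0 | 1.00 | 3.8 / 4.1 | 65% / 60% | 99% / 99% |
| 20%, 0.036 | 1.17 | 5.5 / 5.9 | 41% / 37% | 92% / 88% |
| 30%, 0.036 | 1.22 | 6.4 / 6.9 | 32% / 29% | 84% / 80% |
| 30%, 0.10 | 1.61 | 7.4 / 7.9 | 26% / 23% | 73% / 68% |

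The coefficient-of-variation reading, with kappa 0.036 and the normal value, gives 62%, 45% and 37% power for +5 points at control rates of 10.8%, 20% and 30%. The picture is the same.

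**3. Why case review cannot replace the comparison.** With a 5-point rise, the share of CHARM2-arm cases that are excess is 5/15 = 33%, 5/25 = 20% or 5/35 = 14% at background rates of 10%, 20% and 30%. Nothing marks which cases they are.

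**4. Withdrawals.** For missing endpoints, section 9 says "these will be multiply imputed from the lower (worse) half of the distribution from their arm". For a yes/no event below 50%, that means an imputed event probability of twice the observed rate. Suppose true rates are 25% vs 20% and withdrawals, all of them events, are 3% vs 1%. CHARM2: 22 + 3 × 2 × 22/97 = 23.4%. Control: 19 + 1 × 2 × 19/99 = 19.4%. The estimated rise is 4.0 points instead of 5.

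**5. Disclosure.** With no true change, disclosure of 80% in one arm and 70% in the other creates a false difference of 0.10 × p: 1 point at p = 10%, 3 points at p = 30%.

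**6. Composite.** If MSV falls from 10.8% to 4.8% and physical violence rises from 20% to 25%, any violence moves from 30.8% to 29.8% when the two do not overlap. That apparent fall of 1 point hides a 5-point rise.

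**The case against.** **The item is not confirmed.** The survey instrument is not in the documents. The one sentence naming physical violence covers interviews and surveys together, and section 18 allows items to be dropped after piloting. This stands. A reader might infer that the data are certain to exist and only await analysis; the text makes a recurring item likely (sections 15 and 18 place marital violence and male abuse questions in the wives' survey) but does not establish it.

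**Safeguards are substantial.** A reader might infer that physical violence short of a threat to life is ignored, or that the DSMB will not see violence by arm. Neither is supported. Section 15 provides support for any woman identified as a victim, and nothing bars the DSMB, whose members include MSV and trial experts, from asking for by-arm data. Section 15 also announces internal and external monitoring procedures and a halting plan, but the list does not follow in the available text. What remains is that no by-arm violence measure is specified, and none of the described routes gives a randomised comparison.

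**The table would often miss a modest rise.** Correct: power for 5 points is 23% to 65% across the scenarios, and differential disclosure could add 1 to 3 points of bias either way. The gain is an estimate with an honest interval, not reliable detection.

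**Sexual violence is already compared, and efficacy is untouched.** True, but MSV is expected to fall and cannot stand in for physical violence.

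**Conclusion.** The point holds as a gap in the safety evidence. Violence against wives is a named risk with a route specific to CHARM2, wives are said to be asked about physical violence, and only MSV is compared between arms. As written, the trial has no planned randomised estimate of whether physical violence rose or fell.

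It would be too strong to say that the planned conclusions on contraception, MSV or pregnancy are compromised; they are not affected. It would also be too strong to say that a by-arm table would reliably catch a modest increase. With half-widths of about 4 to 8 points, it would usually show or exclude a rise near 10 points and would often be inconclusive near 5.

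These figures rest on the assumed control rates, village size and kappa. The change is worth making, with medium confidence because the survey item is unconfirmed.

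**What to change.** In section 9, Data Analysis, pre-specify wife-reported physical violence by the husband as a safety outcome.
- Report it by arm at baseline, 9 and 18 months, with the arm difference and a two-sided 95% confidence interval from the cluster-aware model. Use a small-sample correction for 10 clusters per arm and make no significance claim.
- Show it separately from MSV; any composite should be supplementary.
- Report withdrawals for life-threatening violence by arm, with a sensitivity analysis counting these women as having had the event.

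In section 15, Interim Safety and Efficacy Review, state that the DSMB receives these tables at its yearly review. Keep the case review in section 18: both arms answer the survey, so an arm comparison cannot see violence that the survey itself provokes.

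**Cost.** A few sentences and one safety table, with no extra participants or visits and no change to the primary analyses. It requires a physical-violence item at each survey with a recall period that falls within follow-up; if the instrument lacks one, one item must be kept or added. The report should say that an inconclusive interval does not show safety. It should also say that disclosure may differ by arm, because CHARM2 wives receive gender-equity counselling and section 11 leaves research staff unblinded.
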